4.2 Exclusion Criteria and Rationale

Criteria

Exclusion Criteria

- Glasgow Coma Motor Score (GCMS) = 6
- LAR does not speak English or Spanish
- Duration of CPR > 60 minutes
- Severe hemodynamic instability requiring continuous infusion of epinephrine or norepinephrine of 2 µg/kg/minute or initiation of ECMO
- Pre-existing severe neurodevelopmental deficits with PCPC =5 or progressive degenerative encephalopathy
- Pre-existing terminal illness, unlikely to survive to one year
- Cardiac arrest associated with brain, thoracic, or abdominal trauma
- Active and refractory severe bleeding prior to randomization
- Extensive burns or skin lesions incompatible with surface cooling
- Planned early withdrawal of life support before 120 hours
- Sickle cell anemia
- Pre-existing cryoglobulinemia
- Non-fatal drowning in ice covered water
- Central nervous system tumor with ongoing chemotherapy
- Previous enrollment in P-ICECAP trial
- Prisoner
- Chronic hypothermia
- New post-cardiac arrest diabetes insipidus
- Pregnancy

Rationale for selected eligibility criteria - Exclusions:

Participants with GCMS of 6 lack evidence of brain injury and are outside the scope of this trial.

Legally authorized representative (LAR) does not speak English or Spanish is excluded because the VABS-3 is not available in other languages.

Participants with OHCA CPR duration of >60 minutes are expected to have profound brain injury and may not benefit from hypothermia.

Severe hemodynamic insufficiency requiring high vasoactive doses or ECMO and/or ECMO during CPR to achieve return of circulation for OHCA is associated with very high mortality and is not offered at many hospitals.

Several pre-existing conditions may confound the outcome determination. Examples include participants with severe baseline neurodevelopmental deficits (PCPC =5) would likely not have measurable changes in VABS-3 except for death.

A progressive, degenerative encephalopathy may lead to worsening by the time the primary outcome is assessed independent of the intervention.

Patients with preexisting terminal conditions would not be able to contribute outcome data if they are not expected to survive to the one year neurological outcome assessment.

Severe trauma raises concern for exacerbating hemorrhage. Cooling for treatment of severe head trauma has been studied previously and had no benefit on patient outcome.

Planned early withdrawal of life support will not allow completion of the intervention and/or outcome determination.

Certain conditions may contraindicate cooling. Since patients need to be cooled prior to enrollment in P-ICECAP these are unlikely. Some examples include sickle cell anemia and cryoglobulinemia which may be exacerbated by cooling.

[figure not shown]
Prisoners are a vulnerable population.

New post arrest diabetes insipidus is a marker of profound and irreversible neurologic injury and may not benefit from hypothermia.

Patients with chronic hypothermia live at a lower temperature and the intervention may be no different than their baseline.

Patients who are pregnant are excluded given insufficient information to address whether there are reasonably foreseeable risks from trial participation to the pregnant person and fetus, and insufficient literature on the risks and benefits of targeted temperature management in pregnant people. Few, if any, pregnant people would have been anticipated to enroll in the trial, and the trial would be unable to specifically inform use and duration of targeted temperature management in this population. For these reasons, FDA has requested exclusion of pregnant patients.

4.3 Study Enrollment Procedures

The on-call P-ICECAP study team will respond to the PICU clinical team’s notification to screen survivors of OHCA for eligibility, engage eligible patient’s LAR in an informed consent process, coordinate with the clinical care team, and randomize eligible participants. Enrollment case report forms will be completed in the PICU, where the study teams will determine and identify the sources for the times of arrest. Of note, this is routine information obtained by transport teams, pediatric emergency medicine specialists, and pediatric intensivists who care for children after OHCA.

The study team will follow each enrolled participant daily until day 10 for data collection and shepherding of clinical standardization through ICU stay. There is additional data collection at hospital discharge, and the follow up assessments at 3 and 12 months. P-ICECAP will use strategies described in THAPCA-OH that achieved a 98% one-year follow-up success rate (Gildea, 2020).

A screen log that includes all patients with a PICU diagnosis consistent with OHCA (ICD-10 code of I-46, I-46.2, I-46.8, I-46.9, I-49.01, I47.2, R95, R96, R98, R99, or equivalent codes in another diagnostic system) that are treated in the PICU but not enrolled will be completed at all sites.

4.4 Consent Process

Because eligible participants for this study will be comatose children, the informed consent process will be conducted with the patient's LAR (usually parent) as defined by prevailing local law or regulation. During this process the LAR will receive a verbal explanation of the purpose of the study, the scientific basis for hypothermia as a neuroprotectant, the randomization process, the process of temperature management, and the follow-up examinations expected. The specific risks of participating will be outlined. The LAR will be informed that therapeutic hypothermia has not been identified to be of greater benefit than controlled normothermia. The LAR will be informed that the optimal duration of hypothermia has not yet been determined, participation is completely voluntary, and declining to participate will not adversely affect their loved one's care. A discussion of goals of care and intent to maintain life support for 120 hours will also be part of this process as discussed in the eligibility section. Those choosing to enroll their loved one will sign an informed consent document. Because the primary outcome is only available in English or Spanish, only participants with a LAR speaking these languages will be eligible for P-ICECAP. The SIREN Network has a standardized operating procedure for electronic consent or "e-consent" (available at the website <http://siren.network> under "Resources – Standard Operating Procedures.") SIREN uses an e-consent process that is 21 CFR part 11 compliant.

4.4.1 Parents and legally authorized representatives

Some participant information collected will refer to the parents (demographics, socioeconomic status, etc.) and the consent form notes this. Although these data involve others, we still consider these data to be participant information, and do not consider the parents themselves to be participants in the trial. The risk-to-others from collecting these data are low and are adequately managed by the confidentiality protections offered through the participant's enrollment. Additionally, parents can decline to answer specific questions or instruments and still continue with the study.

4.4.2 Change in guardianship

If at any point during the trial, a change in guardianship occurs and/or a participant reaches the age of majority and regains capacity for research decision-making, the new LAR and/or adult participant will be offered the

opportunity to withdraw from the trial and the informed consent process will be repeated. The consent by the new LAR and/or “adult” participant will be obtained using the written informed consent form approved by the IRB and documented in accordance with 21 CFR 50.27(a).

The desire of an LAR or a participant to withdraw from the study will be honored and does not require the LAR or participant to sign any documentation.

4.4.3 Assent from minors

The trial does not require written documentation of the assent of the participating child. No eligible participant will have capacity to assent during the phases of intervention. During follow up assessments, it is anticipated that participants will be asked for their permission to be examined or asked questions, but the trial does not require documentation of this permission. The trial has prepared informative documents that can be optionally used by sites to document assent to continue in the trial and perform these follow up assessments if desired or locally required. These participant facing materials will be approved by the IRB for this optional use.

4.4.4 Withdrawal from study

Altering the allocated intervention duration or declining some surveys is not considered withdrawing from the research study. However, if a parent, LAR, or eligible minor wishes to withdraw fully from the study, data collection will stop at that point in time. Data collected prior to that point, however, cannot be removed from the database as it is safety data in an FDA regulated device trial unless relevant local regulations or laws supersede FDA regulation.

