6.2 Safety Outcomes

The primary safety outcome is all-cause mortality at 30 days. All-cause mortality is selected because it incorporates the most severe irreversible safety consequences across many potential adverse events. Safety problems that are not reflected in either neurological recovery (the efficacy outcome measure) or mortality (the primary safety measure) do not generally cause any permanent morbidity and are therefore secondary. In THAPCA-OH 28-day mortality was used and trended lower in the hypothermia group than normothermia group (57% vs. 67%; $p=0.08$) (Moler, 2015). In THAPCA-OH the most common cause of death was brain death or severe neurologic injury occurring in approximately 80% of both groups.

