6.3 Secondary and Exploratory Efficacy Measures

Secondary Measures – Global Functioning. The Pediatric Cerebral Performance Category (PCPC) and Pediatric Overall Performance Category (POPC) (Fiser, 1992) are 6-point categorical rating scales that include death in the scaling (range normal =1 to death =6). The PCPC rates neurological functioning, whereas the POPC rates

overall health. These scales were included in the 1995 Pediatric Utstein template of recommended guidelines for reporting outcomes of pediatric advanced life support (Perkins , 2015) and have been used extensively to measure CA outcomes (Moler , 2009; Moler , 2015; Sparrow , 2005; Topjian , 2008; Andersen , 2015; Matos , 2013). Most recently, the PCPC was recommended as part of the core outcome set for pediatric cardiac arrest research (Topjian , 2020). The PCPC and POPC will be collected based on review of medical record and caregiver interview within 24 hours of admission for baseline score, and at hospital discharge or at day 30, whichever is first (Topjian , 2020). Age-appropriate PCPC/POPC rating instructions, developed for the THAPCA trials, will be provided to ensure consistent ratings across sites. PCPC/POPC will also be scored at 3 and 12 months by the P-ICECAP neuropsychologist (BS) based on the VABS-3 interview responses. The change in PCPC score from 12 months minus baseline (delta PCPC) will be evaluated.

Neurological Functioning. At 12 months, survivors will undergo a neurological evaluation at their local site. Neurologists will describe the findings of a detailed age-appropriate neurological exam and provide global scores (from 0, normal, to 3, severe impairment) in 7 domains (total score range: 0-21), using the Pediatric Resuscitation after Cardiac Arrest (PRCA) measure, which was adapted from the Pediatric Stroke Outcome measure. PRCA scores obtained in THAPCA were strongly correlated with the VABS-II scores; 16/75 OHCA survivors had normal neurological exams (score “0”) (Ichord , 2018). Motor function in P-ICECAP will primarily be assessed by this measure. Deaths will be assigned the worst score, 21.

Survival at 12 months. Survival status is a standard outcome reported in cardiac arrest trials (Topjian , 2020).

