7.1 Adverse Event Recording

All non-serious AEs occurring through 120 hours from setting the temperature control device to the assigned target and all serious adverse events (SAEs) occurring until participation in study has ended are recorded on the AE case report form (CRF) through the WebDCU™. The Site PI or Study Coordinator or designee is responsible for entering any and all AEs and SAEs into the database as soon as he/she becomes aware of the event and updating the information (e.g., date of resolution, action taken) in a timely manner. All non-serious AEs occurring through 120 hours must be recorded on the electronic AE CRF within 5 days from the time it was discovered by the site study personnel. For SAEs, the data entry must take place within 24 hours of discovery of the event. The NCI Common Terminology Criteria for Adverse Events (CTCAE) (see MoP) will be used to define severity of events.

The Site PI is responsible for the monitoring and follow-up of AEs until resolution or establishment of a new baseline and appropriate documentation in the participant research record. In addition to performing protocol-specified follow up, the participating PI must review all previously reported ongoing AEs to evaluate the current status. Upon completion of the study protocol by the participant, premature withdrawal from the study by the participant, or participant's death, all information regarding each AE must be completed, if not done so earlier.

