9.8 Intention to treat and missing data

The primary analyses will be based on the intent-to-treat ITT population. The ITT population will include all participants randomized, where participants will be included in the treatment arm to which they were randomized, regardless of the duration of cooling applied. Operational procedures are optimized to minimize losing participants to follow up and to prevent missingness of data. Previous experience in the THAPCA Trials by the investigative team demonstrated very low rates of missing data. Any participants that are missing or withdraw from the study and have an unknown 12-month outcome will be included in the analyses of the primary endpoint with multiple imputation according to the longitudinal model previously described.

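### Full withdrawal stops all data collection with no exception for survival status, although death is the zero of the primary score and 30-day mortality is the primary safety outcome

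*Protocol*

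**What the plan says.** Section 4.4.4 separates two situations. Partial refusal leaves the child in the study: "Altering the allocated intervention duration or declining some surveys is not considered withdrawing from the research study". Full withdrawal does not: "if a parent, LAR, or eligible minor wishes to withdraw fully from the study, data collection will stop at that point in time". What is already in the database stays there: "Data collected prior to that point, however, cannot be removed from the database as it is safety data in an FDA regulated device trial", subject to local law. Nothing provides for learning later whether the child lived. Under section 4.4.2, withdrawing needs no signed document.

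The outcomes that depend on survival are set elsewhere. Sections 6.1 and 9.1 score a death as 0 on the VABS-3 Mortality Composite Score. Section 6.2 states: "The primary safety outcome is all-cause mortality at 30 days". Section 6.3 adds survival at 12 months. The schedule in section 6.4 lists all-cause mortality at 30 days, 3 months and 12 months.

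Section 3.3 says that neither the care team nor the family can be blinded to the duration of cooling; the primary outcome assessor is blinded. Section 9.8 defines the ITT population as everyone randomized and adds: "Any participants that are missing or withdraw from the study and have an unknown 12-month outcome will be included in the analyses". The method is multiple imputation from the longitudinal model of section 9.3.2, a simple linear regression of the 12-month score on the 3-month score.

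**The concern.** For every child who dies, vital status alone fixes the primary score, and it is the whole of the primary safety outcome. It can often be learned without contacting the family. A rule that ends its collection gives up the cheapest and most informative item in the trial.

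The loss need not be even across arms, because those who decide on withdrawal know the allocation. If withdrawals cluster in some durations and differ in survival from the children who remain, the arm means are biased. So is everything computed from them: the randomization weights updated about every 10 weeks (section 9.4), the stopping rules (9.5), the selected duration and mortality by arm. An analysis plan can choose how to impute, but it cannot recover a death that the protocol says not to record.

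**Working it through.** **1. What is lost, by time of full withdrawal** (sections 4.4.4, 6.1, 6.2, 9.3.2)

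- Before day 30: observed 30-day mortality and the observed 12-month composite.
- From day 30 to 3 months: the 12-month composite. The 3-month score is missing too.
- After the 3-month assessment: the 12-month composite only. The 3-month score is available to the imputation.

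In the first two cases the stated regression has no predictor value for that child, and section 6.1 says that no baseline VABS-3 is taken. Section 7.1 does not fill the gap, since it records serious adverse events only until participation ends.

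**2. The plan's own effect size** (section 9.7 and Table 9.7.A)

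Composite mean = survival × mean VABS-3 in survivors + (1 − survival) × 0.

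- Control: 0.45 × 65 = 29.25 (stated 29.3).
- Treated: 0.55 × 75 = 41.25 (stated 41.3).
- Difference: 41.25 − 29.25 = 12.0 (stated 12).

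The figures reproduce. The simulated power and type I error were not recomputed, and this point does not depend on them.

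**3. Sensitivity to unknown survival**

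The withdrawal rate w is not in the protocol, so 1% to 10% per arm is assumed. Each early withdrawal is taken as imputed at its arm mean.

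- If all treated withdrawals in fact died, the treated mean is too high by w × 41.25.
- If all control withdrawals in fact survived with the average survivor score, the control mean is too low by w × (65 − 29.25) = w × 35.75.
- With both together, the difference is wrong by w × (41.25 + 35.75) = w × 77.0.
- 30-day mortality in an arm can lie anywhere in a band 100w percentage points wide.

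| w | Children of 900 | Treated mean too high | Control mean too low | Error in difference | Share of 12 units | 30-day mortality band, points |
|---|---|---|---|---|---|---|
| 1% | 9 | 0.41 | 0.36 | 0.77 | 6% | 1 |
| 2% | 18 | 0.83 | 0.72 | 1.54 | 13% | 2 |
| 5% | 45 | 2.06 | 1.79 | 3.85 | 32% | 5 |
| 10% | 90 | 4.13 | 3.58 | 7.70 | 64% | 10 |

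(Columns are rounded separately.)

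These are all-or-none extremes in opposite directions in the two arms, not expected values.

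**4. With survival status known**

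Where status is found, the 30-day mortality band closes to 0 and each death is scored 0 as observed. For children known to be alive, only the VABS-3 remains to be imputed.

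**The case against.** The strongest reply is that the protocol already handles the most likely case. A family unhappy with its allocation need not withdraw: section 5.3 allows the clinical team and parents to alter the depth and duration of cooling, and section 4.4.4 says that this is not withdrawal. Such a child stays in follow-up with mortality recorded at all three time points. This stands, and it confines the problem to families who refuse all further participation.

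Numbers are also likely to be low. Section 4.3 cites 98% one-year follow-up in the prior pediatric trial (section 6.3 gives it for survivors), and that 2% covers loss from every cause, not only early full withdrawal. This stands too.

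Third, how to impute a child without a 3-month score, or a missing 30-day mortality, belongs to the SAP. That is right, and it is not held against the protocol here. It does not answer the main point, which concerns what is collected.

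Two stronger readings are tempting but unsupported:

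- A reader might infer that three withdrawals in an arm of 100 could move its mean by 3 × 65/100 = 1.95 points, as much as a step between neighboring arms in the hypothesized scenario. That ignores the imputation in section 9.8. With 3% imputed at the arm mean, the extremes are 0.03 × 29.25 = 0.88 to 0.03 × 41.25 = 1.24 points if all died, and 0.03 × 33.75 = 1.01 to 0.03 × 35.75 = 1.07 if all survived. Conclusions also come from a curve fitted across all arms (section 9.3.1), not from neighboring pairs.
- A reader might infer that declining the VABS-3 interview leaves nothing to inform the missing score, because PCPC and POPC at 3 and 12 months are rated "based on the VABS-3 interview responses". But that family has not withdrawn. Mortality at all three time points, PCPC/POPC at discharge or day 30, PedsQL and the 12-month PRCA examination all remain (sections 6.3 and 6.4).

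**Conclusion.** The point holds as a weakness in a design choice; it is not a contradiction in the protocol. Followed as written, section 4.4.4 discards survival status after full withdrawal, in an open-label trial whose primary score and primary safety outcome both turn on death.

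The likely effect is small. At an assumed 2% early full withdrawal, 30-day mortality is uncertain by 2 points per arm and the worst-case error is about 1.5 of 12 units; at 5%, 5 points and about 3.9 units. These figures rest on an assumed rate that is equal in both arms, imputation at the arm mean, survivors at their average score, and opposite extremes of survival in the two arms. The case for change is that the remedy is cheap and the loss cannot be repaired afterwards. The consent form was not available; if it already permits survival follow-up after withdrawal, section 4.4.4 should be brought into line with it.

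**What to change.** Amend section 4.4.4 and the matching consent wording:

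- Full withdrawal ends study procedures and contact with the family. Survival at 30 days, 3 months and 12 months is still taken from publicly available records where law allows.
- Before full withdrawal is recorded, the family is offered a limited withdrawal that stops procedures and contact but keeps chart review and survival status.
- Add to section 9.8 that a known death after withdrawal is scored 0, and that imputation is confined to children known to be alive or whose status is still unknown.

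The cost is IRB review of the revised consent text and a record search for a few children. No new visit or assessment is needed, because the three time points are already in the mortality schedule. The change helps only withdrawals that come after it, so it should be made early.

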4.5 Randomization Process

The objective of participant randomization is to prevent possible selection bias by providing random treatment assignment to each participant and to prevent accidental treatment imbalances for the known prognostic variables.

Randomization will be conducted through the web interface of the WebDCU™, the clinical trial management system used for P-ICECAP. The randomization process will be blind to study team members except as needed to perform essential functions. The unblinded statistical team will have access to the randomization information to oversee quality control of the computer program.

4.6 Pregnancy

Participants of childbearing potential cannot be randomized until a pregnancy test is negative.

5. STUDY INTERVENTIONS

5.1 Interventions, Administration, and Duration

The intervention will be random allocation to duration of cooling after cardiac arrest, inclusive of a duration of no additional cooling (controlled normothermia) where the participant is set to a normothermic target after randomization. Cooling in the study will be by a definitive temperature control method to a target temperature of 33°C. Any FDA cleared surface temperature control device with closed loop feedback (servo regulated) will be allowed. Duration of cooling will be measured from the time that cooling is started as indicated by activation of a definitive cooling device (see 5.2 for definition) set to a target of 33°C (targets from 32- 34°C and maintained continuously prior to randomization also qualify as start of cooling). Sites are required to set the target temperature to 33°C within 15 minutes of randomization. Sites are required to have participant temperature below 34°C within 120 minutes of randomization. The constant practice seen in the THAPCA-OH trial was that 70% of pediatric OHCA cases were transported directly from outside community hospitals directly to the Pediatric ICU of the study site. For the remaining 30% of cases coming directly to the study site emergency department, the pediatric patients were resuscitated and if ROSC was achieved, these patients were transferred promptly to the PICU. On arrival to the PICU, arterial and central venous access were rapidly established, and targeted temperature management was initiated. In P-ICECAP, after the allocated duration of cooling is completed, controlled rewarming will be performed. Slow rewarming to a temperature of 36.8°C will occur over approximately 16 hours for those participants assigned to cooling durations greater than zero. After rewarming, a normothermic target will be used until 120 hours from device being set to the hypothermic target (see figure in section 4.3 above).

Participants assigned to no additional cooling (controlled normothermia) will have their target set to normothermia after randomization. Participants assigned to this arm will be rewarmed promptly per routine clinical practice, and will not be rewarmed using the 16 hour procedure for the arms that receive therapeutic hypothermia for 12 to 96 hours. Duration of controlled normothermia will be 120 hours from the time the device is set to a normothermic target. Definitive cooling devices may be used for maintenance of normothermia after rewarming is complete if the participant remains intubated and mechanically ventilated.

